1.3 SCHEDULE OF ACTIVITIES

Table 1 Schedule of Activities

	Screening	Pre-Rand. Visit	Blinded Treatment Period						Safety Follow-Up ^a	Early Discont. ^{b, c}
Week			0	2	4 ^d	6	9 ^d	12	14	
Study Day(s)	-28 to -1	-7 to -1	1	14	28	42	63	84	98	
Visit window (days)				±3	±3	±3	±3	±3	-3/+7	
Informed consent ^e	x									
Medical history, demographics, and baseline conditions ^f	x									
Resting-state EEG ^g		x ^h		x		x		x		x ⁱ
Urinalysis ^j	x								x	x
Urinalysis for substance abuse ^k	x		x			x		x	x	x
Serology (HIV, and hepatitis B and C) ^l	x									
Coagulation ^m	x							x		x
Pregnancy test ⁿ	x		x			x		x		x
Weight and height (height to be measured at screening only)	x							x		x
Vital signs ^o	x		x	x		x		x	x	x
PK blood sample ^p				x		x		x		x
Clinical genotyping sample ^q			x							
Blood sample for WGS ^r			x							
RBR blood sample (optional) ^s				x						

Table 1 Schedule of Activities (cont.)

	Screening	Pre-Rand. Visit	Blinded Treatment Period						Safety Follow-Up ^a	Early Discont. ^{b, c}
Week			0	2	4 ^d	6	9 ^d	12	14	
Study Day(s)	-28 to -1	-7 to -1	1	14	28	42	63	84	98	
Visit window (days)				±3	±3	±3	±3	±3	-3/+7	
Complete physical examination ^t	x		x					x	x	x
Limited physical examination ^t						x				
Neurologic evaluation (upper and lower limbs)	x		x			x		x	x	x
Clinical signs and symptoms of infection ^u					x	x	x	x		
12-Lead ECG ^v	x		x	x				x	x	x
Hematology ^w	x		x			x		x	x	x
Full serum chemistry ^x	x		x			x		x	x	x
Quantitative immunoglobulins (IgA, IgG, IgM, and IgE)			x					x		x
PCL-5	x		x	x		x		x		x
SCID-5	x									
LEC-5	x									
CAPS-5 (administered by central rater)		x ^h				x		x		x
CGI-S			x			x		x		x
CGI-C						x		x		x
PGI-S			x			x		x		x
PGI-C						x		x		x

Table 1 Schedule of Activities (cont.)

	Screening	Pre-Rand. Visit	Blinded Treatment Period						Safety Follow-Up ^a	Early Discont. ^{b, c}
Week			0	2	4 ^d	6	9 ^d	12	14	
Study Day(s)	-28 to -1	-7 to -1	1	14	28	42	63	84	98	
Visit window (days)				±3	±3	±3	±3	±3	-3/+7	
Beck Anxiety Inventory			x			x		x		
Pittsburgh Sleep Quality Index			x			x		x		
PHQ-9			x			x		x		x
C-SSRS ^y	x	x	x	x	x	x	x	x	x	x
SDS			x			x		x		
CPFQ			x			x		x		
Computerized cognitive battery		x ^h		x		x		x		x
Wearable heart rate, step count, and sleep monitoring device (e.g., OURA™ Ring)		x ^z	x	x	x	x	x	x		x
Previous and concomitant medications ^{aa}	x		x	x	x	x	x	x	x	x
Adverse events ^{bb}	x	x	x	x	x	x	x	x	x	x
Study drug dispensation ^{cc}			x			x				
Study drug accountability				x	x	x	x	x		x

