Table 1 Schedule of Activities (cont.)

CAPS-5=Clinician-Administered PTSD Scale for Diagnostic and Statistical Manual of Mental Disorders, Version 5; CGI-C=Clinician Global Impression of Change; CGI-S=Clinician-Global Impression of Severity; CPK=creatine phosphokinase; CK-MB=creatine kinase-MB; CPFQ=Cognitive and Physical Functioning Questionnaire; C-SSRS=Columbia-Suicide Severity Rating Scale; cTnl=cardiac troponin; DSM-5=Diagnostic and Statistical Manual of Mental Disorders, Version 5; eCRF=electronic Case Report Form; EEG=electroencephalogram; HBcAb=hepatitis B core antibody; HBsAg=hepatitis B surface antigen; HCV=hepatitis C virus; HDL=high-density lipoprotein; hs-cTnT=high-sensitivity-cardiac troponin T; LDH=lactate dehydrogenase; LDL=low-density lipoprotein; LEC-5=Life Events Checklist for DSM-5; PCL-5=PTSD Checklist for DSM-5; PCP=phencyclidine; PGI-C=Patient Global Impression of Change; PGI-S=Patient Global Impression of Severity; PHQ-9=Patient Health Questionnaire-9; PK=pharmacokinetic; PTSD=post-traumatic stress disorder; QTc=corrected QT interval; Pre-Rand=randomization; SCID-5=Structured-Clinical Interview for DSM-5; SDS=Sheehan Disability Scale; RBR=Research Biosample Repository; UV=unscheduled visit; ULN=upper limit of normal; WGS=whole genome sequencing.

Notes: On treatment days, all assessments should be performed prior to dosing, unless otherwise specified.

The visit window is ± 3 days, and all assessments should be completed within the visit window. *Following any visit that may occur outside of allowable visit window*, participants should return to the initial planned schedule (per randomization *as Day 1*) for all subsequent visits. For participants who terminate early, assessments listed under the early discontinuation visit should be completed. For safety follow up, the visit window is $-3/+7$ days and all safety assessments should be completed within the visit window.

Unscheduled visits may be performed if clinically indicated. The following assessments should be performed at a minimum: concomitant medications, adverse events, and vital signs. Additional safety assessments may be performed as clinically indicated, per investigator discretion.

- ^a A safety follow-up visit must occur for all participants at 2 weeks following their last study treatment dose.
- ^b To be conducted if a participant discontinues from the study or study-drug treatment prematurely.

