- ^c All participants who withdraw or discontinue from the study treatment early will be asked to return as soon as possible (and within 2 weeks after the last dose of study drug) for an early discontinuation visit, unless the withdrawal occurs within 2 weeks of the Week 12 visit.
- ^d Participants will be called by the site personnel to monitor safety and tolerability when not attending the clinic. *In the event that the participant cannot be reached, at least 3 documented attempts to contact the participant for these visits must occur.*
- ^e Informed consent must be documented before any study-specific screening procedure is performed, and may be obtained more than 28 days before initiation of study treatment.
- ^f Medical history includes clinically significant diseases, surgeries, reproductive status, smoking history, use of alcohol and drugs of abuse, and all medications (e.g., prescription drugs, over-the-counter drugs, vaccines, herbal or homeopathic remedies, nutritional supplements) used by the participant within 24 weeks prior to the screening visit as well as details of psychosocial or non-pharmacological interventions used during the previous 24 weeks. Demographic data will include age, sex, and self-reported race/ethnicity. Participants will also be asked about their residential setting, school, or employment status, level of education, participation in educational or day programs, and any non-medical hospitalizations.
- ^g EEG: Two runs each of resting eyes open and eyes closed.

Table 1 Schedule of Activities (cont.)

- ^h These assessments should be completed no more than 7 days prior to the baseline visit and will be considered the baseline measure.
- ⁱ EEG to be conducted if a participant discontinues study treatment before Week 6.
- ^j Urinalysis will be performed at the site by dipstick for blood, protein, glucose, ketones, specific gravity, and pH. Microscopic examination performed at the central laboratory if blood and/or protein results are positive or strongly positive. If there is an explanation for the positive dipstick results (e.g., menses), it should be recorded and there is no need to perform microscopy and culture.

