7.1 DISCONTINUATION OF STUDY TREATMENT

It may be necessary for a participant to permanently discontinue (definitive discontinuation) study treatment. If study treatment is definitively discontinued, the

participant will remain in the study for additional assessments. Refer to the schedule of activities (see Section 1.3) for data to be collected at the time of discontinuation of study treatment and for any further follow-up evaluations that need to be completed.

Participants must permanently discontinue study treatment if they experience any of the following:

- Any medical condition that the investigator or Sponsor determines may jeopardize the participant's safety if he or she continues to receive study treatment
- Investigator or Sponsor determination that treatment discontinuation is in the best interest of the participant
- Pregnancy
- Inability of participant to continue to comply with study requirements
- Suicidal ideation score of 4 or 5 or category 6 or greater on the C-SSRS
- Specific events that are described in Sections 7.1.1, 7.1.2, 7.1.3, and 7.1.4

The primary reason for study treatment discontinuation should be documented on the appropriate eCRF.

All participants who withdraw or discontinue from the study treatment early will be asked to return as soon as possible (and within 2 weeks after the last dose of study drug) for an early discontinuation visit and complete the assessments as per the schedule of activities in Section 1.3 (see Table 1). Participants will also be asked to return for assessments of the primary and secondary efficacy outcomes at the end of the 12-week planned visit, regardless of their adherence to treatment. If the time between the early discontinuation visit and the 12-week planned visit is fewer than 2 weeks, then participants are exempted from the 12-week planned visit. If the time between the early discontinuation visit and the previous visit is fewer than 2 weeks, then participants are exempted from completing again all the primary and secondary assessments at the early discontinuation visit.

Refer to the schedule of activities in Section 1.3 (see Table 1) for details on follow-up assessments to be performed for participants who permanently discontinue study treatment. If a participant requests to be withdrawn from treatment or follow-up assessments, this request must be documented in the source documents and signed by the investigator.

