9.4.1 General Considerations

For all endpoints, baseline will be defined as the last assessment made up to and including the day of first study drug intake.

In general, descriptive statistics will be used to summarize continuous endpoints and counts and percentages will be used to summarize categorical endpoints.

Missing values will not be replaced.

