9.4.2 Primary Endpoint

The primary endpoint is the change in CAPS-5 total symptom severity score from baseline at Week 12, as defined in Section 3 (see Table 2). The change from baseline in CAPS-5 total symptom severity score at Week 12 will be calculated as the score at Week 12 minus the score at baseline. A negative change from baseline in CAPS-5 total symptom severity score indicates improvement.

Every effort will be made to minimize missing data. Participants who discontinue early from study treatment will be asked to return for collection of safety and limited efficacy data (i.e., the primary and secondary efficacy endpoints) at the scheduled visits.

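### Protocol Section 7.1 and schedule footnote c give opposite visit instructions for participants who stop treatment within about 2 weeks of Week 12, so a Week 12 CAPS-5 may be lost for some of them

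*Combined protocol and SAP*

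**What the plan says.** Three places in the protocol deal with a participant who stops treatment late.

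- **Section 7.1** asks every early discontinuer to return "as soon as possible (and within 2 weeks after the last dose of study drug" for an ED visit. It also asks them back at Week 12 for the primary and secondary outcomes. It then makes an exception: if the interval from the ED visit to the "12-week planned visit is fewer than 2 weeks, then participants are exempted from the 12-week planned visit". Its next sentence excuses participants from repeating the primary and secondary assessments at an ED visit held fewer than 2 weeks after the previous visit.
- **Section 1.3, footnote c to Table 1** asks the same participants to come back "for an early discontinuation visit, unless the withdrawal occurs within 2 weeks of the Week 12 visit". It waives the ED visit and says nothing about waiving Week 12.
- **Section 9.4.2** has discontinuers return for safety and limited efficacy data ("i.e., the primary and secondary efficacy endpoints) at the scheduled visits"). It states no exemption.

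For the analysis, the primary change score "will be calculated as the score at Week 12 minus the score at baseline" (Section 9.4.2). Week 12 is Day 84 with a window of ±3 days, and the schedule notes say that "all assessments should be completed within the visit window". The Table 1 row "CAPS-5 (administered by central rater") is marked at the ED visit as well as at Weeks 6 and 12, and CGI-S and PHQ-9 are marked there too. Section 9.4.1 states: "Missing values will not be replaced". Section 9 contains no rule that assigns an ED assessment to a scheduled visit.

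**The concern.** Section 3 asks for the Week 12 effect whether or not participants kept to their assigned treatment. Late discontinuers are therefore people whose Week 12 outcome the study means to retain. Whether that outcome exists depends on which passage the site follows. Under Section 7.1 the only late CAPS-5 may come from an ED visit several days before the Week 12 window opens, and the plan does not say whether it counts. Under footnote c a Week 12 score should be obtained.

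A site that applied both waivers would have no end-of-treatment CAPS-5 at all. Strictly, the Section 7.1 waiver presupposes an ED visit, so this would be a misapplication, but the texts invite it.

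At stake are a few values in the descriptive Week 12 summaries of CAPS-5, CGI-S and PHQ-9, with about 15 participants per arm. If the handling of these scores is left open, it may be settled after treatment assignments are known. Section 6.3.2 allows some sponsor staff unblinded access during the study.

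**Working it through.** The plan has no figure to reproduce here. Section 9.2 gives 15 + 15 = 30 participants without design inputs, and Section 9.1 tests no hypothesis. The check is day arithmetic, followed by a count under stated assumptions.

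**1. Days affected (Table 1 and its notes; Section 7.1)**

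- Week 12 = 12 × 7 = Day 84; window 84 ± 3 = Days 81–87.
- Section 7.1 waiver: 84 − ED day < 14, so ED on Days 71–83.
- Days 81–83 lie inside the Week 12 window. That leaves Days 71–80, which is 10 of the 13 waiver days.
- If Week 12 is booked at the edge of its window, the range becomes Days 68–80 (booked Day 81) or Days 74–80 (booked Day 87).
- Footnote c: within 2 weeks of Day 84 means withdrawal from Day 70 onward.

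**2. One participant under each rule (last dose Day 75)**

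| Rule | ED visit | Week 12 visit |
|---|---|---|
| Section 7.1, ED held before Day 84 | yes | waived |
| Footnote c | waived | stands |
| Section 9.4.2 | not addressed | stands |

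**3. Is CAPS-5 certain to be done at that ED visit?**

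Not if the Week 9 telephone call (Day 63, no CAPS-5) counts as the previous visit. Then an ED visit with ED day − 63 < 14, up to Day 76, is excused from the primary and secondary assessments. That covers Days 71–76 of the affected range. With Week 9 at the edges of its own window (Days 60 to 66), it covers Days 71–73 to Days 71–79. Footnotes d and cc do refer to the calls as visits. Section 7.1, however, speaks of completing assessments again, which suggests the call was not meant.

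**4. Expected number affected**

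The documents give no discontinuation rate and no distribution of ED delays. Assume that 20–40% of 30 discontinue, that last-dose day *s* is equally likely on Days 1–84, and that ED delay *d* is equally likely on 0 to *D* days. Count the pairs with *s* + *d* in 71–80 out of 84 × (*D* + 1).

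| *D* | Section 7.1 governs | Footnote c governs (*s* < 70 only) |
|---|---|---|
| 3 | 40/336 = 11.9% | 3/336 = 0.9% |
| 7 | 80/672 = 11.9% | 21/672 = 3.1% |
| 14 | 150/1260 = 11.9% | 85/1260 = 6.7% |

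Multiply by 30 × 0.2 = 6 and by 30 × 0.4 = 12:

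- Section 7.1 governs: 0.71–1.43 of 30 for any *D*. At a 10% discontinuation rate it would be 3 × 10/84 = 0.36.
- Footnote c governs: 0.05–0.11 (*D* = 3), 0.19–0.38 (*D* = 7), 0.40–0.81 (*D* = 14).

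The footnote c remainder consists of participants who stop before Day 70 but attend a delayed ED visit on Days 71–80. Footnote c does not reach them, and Section 7.1 still waives their Week 12 visit.

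**5. Weight of one value**

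1/15 = 6.7% of an arm. The standard error of a difference in means rises by a factor √[(1/14 + 1/15)/(2/15)] = 1.018, or 1.8%.

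**The case against.** The strongest reply is that the texts can be read together. Footnote c is keyed to the date of withdrawal and Section 7.1 to the date of the ED visit, and Section 7.1 sends the reader to the schedule for what to do at discontinuation. On that reading a withdrawal within 2 weeks of Week 12 means no ED visit and a normal Week 12. Section 7.1 then waives Week 12 only for earlier stoppers whose ED visit happens to fall late. This fits Section 9.4.2 and gives the smaller counts. The reading is reasonable, but nothing states that the footnote prevails, and Section 7.1 asks for an ED visit from all discontinuers without exception. The ambiguity stands, and the larger counts belong only to the reading in which Section 7.1 governs.

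A reader might also infer that the primary value is definitely missing for these participants. The documents do not support that. No section excludes an ED score from Week 12; they are silent on the assignment. The rule against replacing missing values does not itself make a collected ED score missing. Being exempted from Week 12 is also not being barred from it, so a participant may still attend. The supportable statement is that the value may be lost.

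**Conclusion.** The inconsistency is real and minor. For a last dose around Day 75, Section 7.1 and footnote c lead to different visits, and Section 9.4.2 recognises no exemption. On the Section 7.1 path an ED CAPS-5 on Days 71–80 falls outside the Week 12 window and has no assigned place in the analysis.

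The counts of about 0.7–1.4 of 30 (Section 7.1 governs) and about 0.05–0.8 (footnote c governs) rest entirely on the assumed 20–40% discontinuation, even timing and ED delays. They are expectations, not maxima. If ED visits are held promptly, as Section 7.1 asks, the footnote c figure lies at the low end. Participants who leave the study altogether have an ED visit only where possible (Section 7.2), which lowers the number of collected but unassigned scores.

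A reader might go further and infer that the trial's error rate, power or sample size is compromised. It is not: no hypothesis is tested, and only descriptive Week 12 summaries are touched.

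**What to change.** Reconcile Section 7.1, footnote c of Table 1 and Section 9.4.2 so that one visit rule applies to late discontinuers and a primary and secondary efficacy assessment is always obtained at or near Week 12. In the same edit, make clear that the Week 9 telephone call does not trigger the Section 7.1 exemption for an ED visit held soon after the previous visit.

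Only if the reconciled text still waives Week 12 for some participants, add one sentence to Section 9.4.1, before any review of unblinded data: the ED assessment that triggered the waiver is analysed as Week 12. The downside is a score up to 13 days early (84 − 71). If no waiver remains, the sentence is not needed.

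The cost is aligned wording in three places and at most one added analysis sentence, with no added participants or types of assessment. If the chosen rule keeps Week 12, some late discontinuers attend a visit that Section 7.1 now waives but that is already in the schedule.

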8.1.1.1 Clinician-Administered PTSD Scale for DSM-5 (CAPS-5)

The CAPS-5 is a 30-item structured interview that can be used to make current (past month) diagnosis of PTSD, make lifetime diagnosis of PTSD, or assess PTSD symptoms over the past week (Weathers et al. 2013a, 2018; see [Appendix 11](#)). For this study the past week version of the CAPS-5 will be used and will be administered by central rater. Items are scored using a 5-point scale, rated from 0 (absent) to

4 (extreme/incapacitating), with a higher overall score indicating a worse outcome. In addition to assessing the 20 DSM-5 PTSD symptoms, questions asked target the onset and duration of symptoms, subjective distress, impact of symptoms on social and occupational functioning, improvement in symptoms since a previous CAPS administration, overall response validity, overall PTSD severity, and specifications for the dissociative subtype (depersonalization and derealization). Responses will be collected by means of free text to understand intensity and frequency of symptoms, which are then used to select a response on a 5-point Likert scale, ranging from 0 (absent) to 4 (extreme/incapacitating). A total score is calculated by summing severity scores for items 1–20, where a higher score corresponds to greater severity of PTSD or presence of PTSD. Symptom cluster severity scores can also be derived by summing the individual item severity scores for symptoms corresponding to a given DSM-5 cluster: Criterion B (items 1–5); Criterion C (items 6–7); Criterion D (items 8–14); and, Criterion E (items 15–20). For each symptom, standardized questions and probes are provided. Administration requires identification of an index traumatic event to serve as the basis for symptom inquiry via the Life Events Checklist for DSM-5 (LEC-5; see Section 8.1.1.4 for more detail). The LEC-5 will be administered prior to the CAPS-5 at screening only. The CAPS was designed to be administered by clinicians and clinical researchers who have a working knowledge of PTSD but can also be administered by appropriately trained paraprofessionals.

The full interview takes 45–60 minutes to administer. In this study, the past week version of the CAPS-5 will be administered remotely by a central assessor. This first CAPS-5 assessment will be administered no more than 7 days prior to the baseline and at Week 6 and Week 12.

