8.1.1.2 Clinician-Global Impression of Severity (CGI-S) and Change (CGI-C)

The CGI-S and CGI-C are single items rated by the clinician (Guy 1976; see [Appendix 11](#)). The CGI-S is used to assess the overall severity of PTSD symptoms over the past 7 days, whereas the CGI-C is used to assess change in overall PTSD symptoms from baseline. Each item is rated on a 7-point scale, ranging from 1 (no symptoms/very much improved) to 7 (very severe/very much worse) for the CGI-S and CGI-C, respectively. Clinicians should make a judgment on severity and any changes from baseline based on the totality of information available to them (e.g., insights from the patient captured during the completion of other trial assessments). The assessments will take up to 5 minutes to complete in their entirety. The CGI-S will be collected at baseline, Week 6, and Week 12. The CGI-C will be collected at Week 6 and Week 12.

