8.1.1.3 Patient Health Questionnaire-9 (PHQ-9)

The PHQ-9 is a 9-item PRO used to assess severity of depression over the last 2 weeks. It was developed using each of the 9 DSM-IV criteria. On the basis of these criteria, the diagnosis of depressive disorders is made (Kroenke et al. 2001; see

[Appendix 11](#)). Responses are rated based on frequency of symptoms on a 4-point Likert scale, ranging from 0 (not at all) to 3 (nearly every day). Responses are reported using a recall of the last 2 weeks. A total PHQ-9 total score ranging from 0 to 27 can be calculated by summing the nine items, of which a higher score corresponds to more severe depression. Scores of 5, 10, 15, and 20 represent cutpoints for mild, moderate, moderately severe, and severe depression, respectively. It takes approximately 90 seconds to 3 minutes to complete. The PHQ-9 will be administered at baseline, Week 6, and Week 12.

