8.1.1.5 PTSD Checklist for DSM-5 (PCL-5)

The PCL-5 is a 20-item PRO used to assess the 20 DSM-5 symptoms of PTSD (Weathers et al. 2013c; Blevins et al. 2015; see [Appendix 11](#)). Responses are reported on a 5-point Likert scale, ranging from 0 (not at all) to 4 (extremely). A recall period of one month has been validated. However, the PCL-5 manual acknowledges a recall period of less than one month may make more sense in some cases, but to be aware that the psychometric properties may differ to those published using the one-month recall (National Center for PTSD 2013). In this study, the one-month recall will be used at screening for diagnostic purposes and a one week recall version will be used thereafter for efficacy. This is to allow for more frequent PCL-5 administrations without overlapping recalls. A total severity score, ranging from 0 to 80, can be calculated by summing all items, of which a higher score corresponds to more severe symptoms. The PCL-5 can be used to determine a provisional diagnosis in two ways; either using a cutpoint score of 31 to 33, or alternatively, by treating each item rated as 2 (moderately) or higher as a symptom endorsed and then following the DSM-5 diagnostic rule, which

requires at least: 1 Criterion B item (Questions 1–5), 1 Criterion C item (Questions 6–7), 2 Criterion D items (Questions 8–14), and 2 Criterion E items (Questions 15–20). If a patient meets a provisional diagnosis using either of the methods above, then he or she needs further assessment (e.g., CAPS-5 or SCID-5) to confirm a diagnosis of PTSD. It takes approximately 5–10 minutes to complete. The PCL-5 will be administered at screening, baseline, Week 2, Week 6, and Week 12.

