9.4.3.2 Patient Health Questionnaire-9 (PHQ-9)

The PHQ-9 is a 9-question instrument to assess presence and severity of depression (see Section 8.1.1.3 for details). The total sum of responses score ranges from 0 to 27 and will be summarized using descriptive statistics at each assessment timepoint for absolute values as well as change from baseline. Additionally, the score will be categorized as shown in Table 5, and a shift table will be provided to examine changes in depression severity categories from baseline to worst post-baseline depression severity.

Table 5 Patient Health Questionnaire-9 (PHQ-9) Score and Corresponding Categories

PHQ-9 Score	Depression Severity
0–4	None-minimal
5–9	Mild
10–14	Moderate
15–19	Moderately severe
20–27	Severe

PHQ-9=Patient Health Questionnaire-9

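### The waiver of CAPS-5, CGI-S and PHQ-9 at the early discontinuation visit depends on the date of the previous visit, so some who leave before Week 6 may have no post-baseline primary or secondary score

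*Combined protocol and SAP*

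**What the plan says.** Section 7.1 asks participants who stop early to attend an early discontinuation visit within 2 weeks of the last dose and to complete the assessments listed in Table 1. It then adds a waiver: "If the time between the early discontinuation visit and the previous visit is fewer than 2 weeks, then participants are exempted". The scope is wide, because participants are "exempted from completing again all the primary and secondary assessments at the early discontinuation visit".

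The primary and secondary instruments are scheduled as follows:

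- **CAPS-5 (Section 8.1.1.1):** "This first CAPS-5 assessment will be administered no more than 7 days prior to the baseline and at Week 6 and Week 12".
- **CGI-S (Section 8.1.1.2):** "The CGI-S will be collected at baseline, Week 6, and Week 12".
- **PHQ-9 (Section 8.1.1.3):** "The PHQ-9 will be administered at baseline, Week 6, and Week 12".

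Table 1 also marks all three in the early discontinuation column. The Week 2 visit has an efficacy scale, but it is the exploratory PCL-5 (Section 8.1.1.5: "The PCL-5 will be administered at screening, baseline, Week 2, Week 6, and Week 12"). Weeks 4 and 9 are telephone calls (Section 4.1.2). Table 1 gives them visit windows, and its footnote d calls them visits: "at least 3 documented attempts to contact the participant for these visits must occur".

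Three other provisions matter. Sections 7.1 and 9.4.2 ask those who stop treatment to return for primary and secondary efficacy data, at Week 12 and at the scheduled visits respectively. Section 7.2 ends all participation for those who withdraw from the study. Section 9.4.1 says missing values are not replaced.

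**The concern.** The waiver makes sense only if the previous visit collected the instruments being waived. Before Week 6 no post-baseline visit does. A site that sees a participant for early discontinuation on Day 24 finds the Week 2 visit 10 days earlier and, on the literal wording, omits CAPS-5, CGI-S and PHQ-9. The last CAPS-5 in that case was taken before randomization.

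For someone who withdraws from the study, or who stops treatment and does not come back, this visit is the last chance to record those scores. Without a PHQ-9 score after baseline, the participant cannot enter the table in Section 9.4.3.2 that is meant to "examine changes in depression severity categories from baseline to worst post-baseline depression severity". The report also cannot say, on the primary or secondary scales, how such participants were doing when they left. With 15 participants per arm, each one is 1/15, or about 7%, of an arm.

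**Working it through.** The plan gives no figure to reproduce. The check is a count of days.

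**Inputs.** Nominal days from Table 1: baseline Day 1, Week 2 Day 14, Week 4 call Day 28, Week 6 Day 42, Week 9 call Day 63, Week 12 Day 84. In-clinic and call windows are ±3 days.

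**Rule.** The waiver applies if (early discontinuation visit day) − (previous visit day) < 14. The date that counts is that of the early discontinuation visit, which may fall up to 2 weeks after the last dose.

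**Before Week 6, calls not counted as visits** (previous visit is Day 1 or Day 14):

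- Days 2–13: gap 1 to 12, waived, 12 days.
- Days 15–27: gap 1 to 13, waived, 13 days.
- Days 28–41: gap 14 to 27, not waived, 14 days.
- Total waived: 12 + 13 = 25 of 39 non-visit days (64%).

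**Before Week 6, calls counted as visits** (Day 28 becomes a visit):

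- Days 29–41: gap 1 to 13, waived, 13 days.
- Total waived: 12 + 13 + 13 = 38 of 38 non-visit days.

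When actual visit days vary over the ±3-day windows, the waived share before Week 6 is 52% to 72% if calls do not count and 80% to 100% if they do. On every waived day before Week 6, the most recent score on all three instruments is the baseline one.

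**After Week 6** the rule also waives Days 43–55, and Days 64–76 if the Week 9 call counts. A Week 6 score should exist by then, so these days are not part of the problem.

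**Which trigger closes the gap before Week 6?**

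- *Time since the last CAPS-5 of any kind.* There is no Day 0. A baseline CAPS-5 on Day −7 leaves Days 2–7 waived (6 days), and one on Day −1 leaves Days 2–13 waived (12 days). The same trigger for CGI-S and PHQ-9, with baseline on Day 1, leaves Days 2–14 waived.
- *A post-baseline completion of the same instrument in the previous 14 days.* No day before Week 6 is waived.

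**How many participants?** The documents give no dropout rate, so this is an illustration under assumed values. If 5% to 20% of 30 stop before Week 6 and 25% to 100% of those do not return, the number runs from 30 × 0.05 × 0.25 = 0.4 to 30 × 0.20 × 1.00 = 6. It is lower if calls do not count as visits. It is also lower to the extent that some never attend an early discontinuation visit, since nothing is then waived.

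**The case against.** The best defence is the word *again* in "exempted from completing again all the primary and secondary assessments at the early discontinuation visit". It can be read as limiting the waiver to instruments actually completed at the previous visit, with Table 1 as the default. That is probably what the authors meant. But the sentence gives a site no such test. Its only stated condition is the date of the previous visit, and a participant with a baseline CAPS-5 would in any case be completing it again. The word makes the text ambiguous without restoring collection. Section 7.2 adds to the ambiguity: it refers to Table 1 for the visit at study withdrawal and neither repeats nor disapplies the waiver.

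Several stronger conclusions are tempting, and the documents do not support them:

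- **A reader might infer that early stoppers leave with no efficacy data.** The waiver covers only primary and secondary assessments. PCL-5, CGI-C, PGI-S and PGI-C are exploratory and are still due at the early discontinuation visit, and PCL-5 is also taken at Week 2.
- **A reader might infer that everyone who stops before Week 6 is lost.** Those who remain in the study are asked back under Sections 7.1 and 9.4.2. The loss requires withdrawal or failure to return.
- **A reader might infer bias in the primary result, for instance that an arm looks better because people who worsened are removed.** A pre-Week 6 CAPS-5 or CGI-S would not enter a Week 12 change summary with no replacement of missing values, so collecting it would not alter that summary. Several of the discontinuation triggers in Section 7.1, such as pregnancy, liver tests and QTc, need not relate to PTSD severity.
- **A reader might count the whole treatment period and report 64 of 78 non-visit days (82%).** That figure treats calls as visits and includes 26 days after Week 6.
- **A reader might apply the day ranges to the day treatment stops.** If calls are not visits, a last dose on Day 20 with an early discontinuation visit on Day 30 is 16 days after Week 2 and is not waived.

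**Conclusion.** The point stands as a gap in data collection, and it is worth correcting. As worded, the waiver can remove CAPS-5, CGI-S and PHQ-9 at the early discontinuation visit on 25 of 39 nominal non-visit days before Week 6, or on all 38 if calls are visits. On none of those days has any of the three been scheduled since baseline. The waiver therefore conflicts with Table 1 and with the aim in Section 9.4.2 of minimizing missing data.

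The consequence is limited. It falls on participants who attend the early discontinuation visit and then withdraw or do not return. It touches the PHQ-9 shift table and the description of early stoppers, and leaves the Week 12 CAPS-5 and CGI-S summaries unchanged. This assumes that a score from the early discontinuation visit counts as post-baseline in the shift table, which Section 9.4.3.2 does not exclude. The study is descriptive with no hypothesis test, so no error rate is involved. The documents do not allow the number affected or the direction of any bias to be stated.

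**What to change.** Replace the waiver sentence in Section 7.1 with a rule applied to each instrument, for example: *CAPS-5, CGI-S or PHQ-9 may be omitted at the early discontinuation visit only if that same instrument was completed after baseline within the previous 14 days; otherwise it is completed as scheduled in Table 1.* The condition must say *after baseline*, because a trigger based only on the last CAPS-5 still leaves 6 to 12 waived days. Waivers in the two weeks after a completed Week 6 assessment are kept, and the question of whether a telephone call is a visit no longer matters. A cross-reference in Section 7.2 would make clear that the same rule applies at study withdrawal.

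The cost is one sentence, plus a 45–60 minute remote CAPS-5, a CGI-S and a PHQ-9 for a few early stoppers, at a visit where Table 1 already schedules them. One drawback should be acknowledged: the PHQ-9 looks back 2 weeks, so at an early discontinuation visit in the first 2 weeks its recall partly covers days before treatment. Those scores should be read with that in mind.
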